2.1.2 Secondary objectives

The secondary objectives of the study are to assess:

- The optimal initial treatment dose for the treatment of moderate to severe chronic plaque PSO
- Durability of the clinical response with maintenance treatment
- The safety and tolerability of CZP
- Improvement of skin-related quality of life
- Change from Baseline in Itch Numeric Rating Scale at Week 16

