8.1.2 Primary analysis of the primary efficacy variable

The primary analysis for the PASI75 response at Week 16 will be based on a logistic regression model for the FAS which will include fixed effects for treatment group and prior biologic exposure (yes/no). Prior biologic exposure was selected as a fixed effect in the logistic regression model as it is a stratification variable for randomization and because it may have an impact on efficacy. The odds ratio, associated confidence interval, and p-value

will be presented. If convergence is not obtained due to having only or no responders in one or more treatment groups, then an exact logistic regression will be applied and odds ratio, associated exact confidence interval, and exact p-value will be determined. If the logistic regression model is unable to converge, then prior biologic exposure may be dropped from the model to facilitate convergence. This model is used when the sample size is too small for a regular logistic regression or when some of the cells formed by the outcome and categorical predictor variable have no observation.

The Markov Chain Monte Carlo (MCMC) method for multiple imputation will be used to account for missing values in the primary analysis of PASI75 at Week 16. The multiple imputation procedure for PASI75 will be based on the actual PASI score.

For derivation of PASI75 response, no rounding will be performed. That is, the imputed Week 16 PASI value will be compared directly to the observed Baseline value to determine whether or not a reduction of at least 75% was achieved.

Each CZP dose will be compared against PBO to establish superiority over PBO and will be tested sequentially at an alpha of 0.025 as outlined in Section 4.5.

Multiple imputation and the subsequent analysis will involve the 3 tasks described below:

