As the estimates of the odds ratios from the logistic regression model follow a log-normal distribution, a log transformation is needed to normalize these estimates since the procedures for combining results from multiple imputed datasets are based on the assumption that the statistics estimated from each imputed dataset are normally distributed. Therefore, the log of the odds ratio estimates from the logistic regression model will need to be used when combining into a single inference (the PROC MIANALYZE step). Additionally, the standard errors for the odds ratios are transformed as follows:

$$[\log(\text{UCL}) - \log(\text{LCL})] / (2 * Z_{\alpha/2})$$

where UCL and LCL are the upper and lower confidence limit, respectively, for the confidence interval of the odds ratio from the logistic regression model, and $Z_{\alpha/2}$ is the relevant critical value from the standard normal distribution (based on $\alpha=0.05$ for a 95% confidence interval and $\alpha=0.025$ for a 97.5% confidence interval).

The PROC MIANALYZE step takes the estimates of the log odds ratio and standard errors for each imputation and combines them to derive a single estimate of the log odds ratio and corresponding standard error. The odds ratio is then estimated by exponentiating the estimate of the log odds ratio. The confidence limits of the odds ratio are then estimated as follows:

$$\text{LCL} = \text{OR} * \exp(-\text{SE} * Z_{\alpha/2})$$

$$\text{UCL} = \text{OR} * \exp(\text{SE} * Z_{\alpha/2})$$

where OR is the back-transformed estimate of the odds ratio just described, SE is the standard error of the log odds ratio derived in PROC MIANALYZE, and $Z_{\alpha/2}$ is the relevant critical value from the standard normal distribution (based on $\alpha=0.05$ for a 95% confidence interval and $\alpha=0.025$ for a 97.5% confidence interval). These calculations will be done such that odds ratios and corresponding confidence intervals are calculated for the odds ratio of each CZP dose versus placebo. Note that the p-values presented in the tables will be the ones provided initially by PROC MIANALYZE and are not impacted by the transformations described above.

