In addition to calculating the odds ratio, associated CIs, and p-values for the pairwise comparisons of each CZP treatment group with PBO, the estimated proportion of responders (eg, estimated responder rate) and the difference in the proportion of responders between each CZP treatment group and PBO will be estimated, and 2-sided 95% CIs will be created for each difference. The creation of these estimates will be completed for each CZP treatment group using the process detailed below:

1. Use the logistic regression model to calculate:
 - a. Least squares mean estimates of the log odds of CZP (G_C) and PBO (G_P), as well as their corresponding standard errors (S_C and S_P , respectively)
 - b. Standard error of the least squares mean estimate of the log odds ratio (S_R)
2. Compute estimates for predicted proportions using the following transformations:

$$P_C = \exp(G_C) / (1 + \exp(G_C))$$

$$P_P = \exp(G_P) / (1 + \exp(G_P))$$

The difference in proportions is then given by:

$$D = P_C - P_P$$

3. Estimate the standard error of D by:

$$S_D = \sqrt{P_C^2 (1 - P_C)^2 S_C^2 + P_P^2 (1 - P_P)^2 S_P^2 + P_C (1 - P_C) P_P (1 - P_P) S_R^2 - P_C (1 - P_C) P_P (1 - P_P) (S_C^2 + S_P^2)}$$

The Markov Chain Monte Carlo (MCMC) method for multiple imputation, as previously outlined, will be used to account for missing values of PASI. This method will create multiple complete data sets which may be analyzed with the process described above. An estimate for the difference in proportions, D, and corresponding standard error, SD, will be computed for each complete dataset.

The results from these analyses will be combined into a single 2-sided 95% confidence interval using SAS PROC MIANALYZE.

In cases where one treatment group has either no responders or only responders, exact logistic regression will be used to calculate the odds ratio with its corresponding confidence interval and p-value. The exact logistic regression will include treatment, and prior biologic exposure as in the primary model. The following procedure will be used to obtain these estimates:

1. Obtain the odds ratio and lower 2-sided confidence limit (based on $\alpha=0.05$ for a 95% confidence interval and $\alpha=0.025$ for a 97.5% confidence interval) for each imputation from PROC LOGISTIC using the EXACT statement and ESTIMATE=BOTH option.

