A subject will be classified as a responder at Week 16 if they achieve a PGA score of 0 ('Clear') or 1 ('Almost clear') and they have at least a 2-category improvement relative to Baseline. Note that a PGA score of at least 3 is required per the inclusion criteria, so all subjects achieving a PGA score of 0 or 1 should, by definition, be a responder. However, in the case that a subject with a Baseline score of 2 is mistakenly randomized, then this subject may be classified as a responder only if a PGA score of 0 is achieved (thereby achieving the required 2-category improvement).

PGA response at Week 16 will be analyzed for treatment effects using pairwise comparisons based on the same method as that for the primary efficacy variable.

The MCMC algorithm is based on the multivariate normal model; imputed values for PGA will not generally be one of the discrete values actually used in PGA scoring (0, 1, 2, 3, or 4). Therefore, standard rounding rules will be applied to the imputed values in order to derive the

binary PGA response variable. For example, if a subject has a PGA score imputed as 1.4 (and assuming a Baseline PGA score of 3), this imputed value would be rounded down to 1, and the minimum change from Baseline of 2 would have been met. Therefore, this subject would be considered a responder.

The significance testing of each CZP treatment group vs PBO will be part of the fixed sequential testing procedure described in [Section 4.5](#).

8.2.2 PASI90 at Week 16

PASI90 response at Week 16 will be analyzed for treatment effects using pairwise comparisons based on the same method as that for the primary efficacy variable. Each CZP dose will be compared against placebo to establish superiority over placebo and will be tested at a significance level of 0.025 as part of the fixed sequence testing procedure outlined in [Section 4.5](#).

8.2.3 Change from Baseline in DLQI at Week 16

The Dermatology Life Quality Index (DLQI) is a skin-disease-specific questionnaire evaluating how symptoms and treatment affect patients' Health-Related Quality of Life (HRQoL). This instrument includes 10-questions that cover 6 domains including symptoms and feelings, daily activities, leisure, work and school, personal relationships, and treatment, as assessed over the past week. It is validated and reproducible in PSO patients.

The scoring of each answer for the DLQI is as follows:

Table 8–2: DLQI scoring

Response	Score
Very much	3
A lot	2
A little	1
Not at all	0

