Not relevant	0
Question unanswered	0
Q7: 'prevented work or studying' = yes	3

The DLQI is calculated by adding the score of each question and ranges from 0 to 30 with higher scores indicating lower HRQoL:

Meaning of DLQI Scores

0-1 = no effect at all on patient's life

2-5 = small effect on patient's life

6-10 = moderate effect on patient's life

11-20 = very large effect on patient's life

21-30 = extremely large effect on patient's life

A ≥ 4 -point change in the DLQI score (DLQI response) has been reported to be meaningful for the patient (within-patient minimal important difference); a DLQI absolute score of ≤ 1

indicates DLQI remission (ie, no or small impact of the disease on HRQoL) (Basra et al, 2015).

Because Question 7 (Q7) has a sub-question (referred to as Q7a here) after the leading yes/no question, some clarifying rules for scoring are provided:

- If Q7='yes', then score=3 regardless of the responses to Q7a.
- If Q7='no', 'not relevant', or is missing and Q7a='A lot', then score= 2.
- If Q7='no', 'not relevant', or is missing and Q7a='A little', then score=1.
- If Q7='no', 'not relevant', or is missing and Q7a='Not at all', then score=0.
- If Q7='no', 'not relevant', and Q7a is missing or not applicable, then score=0.
- If Q7 is missing and Q7a is missing, Q7 is considered unanswered (see below for details on how this impacts the overall DLQI score).

If 1 question is left unanswered, this is scored 0 and the scores are summed as usual. If 2 or more questions are left unanswered, the questionnaire is not scored.

The analysis of DLQI will be based on the change from Baseline at Week 16 for the FAS. Treatment group comparisons for each CZP treatment group vs placebo will be performed using an analysis of covariance (ANCOVA) model with treatment group and prior biologic exposure as factors and Baseline DLQI score as a covariate. The least squares (LS) means and standard errors derived from the model will be presented for each treatment group. Additionally, adjusted mean treatment differences, corresponding confidence intervals, and p-values will be reported. Missing values will be imputed using LOCF. Each CZP dose will be compared against placebo to establish superiority over placebo and will be tested at a significance level of 0.025 as part of the fixed sequence testing procedure outlined in [Section 4.5](#).

8.2.4 Change from Baseline in Itch Numeric Rating Scale at Week 16

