3. For the subjects meeting the escape criterion identified in Step 1, all visits after the point of escape will be imputed via NRI. This imputation is based on meeting the escape criterion, whether or not the subject actually received escape treatment. Once imputation has been performed for these subjects, these records are duplicated 75 times and combined with the 75 imputations performed in Step 2.

Note: If subjects identified here have intermittent missing data at earlier time points, those will be imputed via NRI.

4. For each complete imputed data set, the dichotomous PASI responder rate based on the PASI scores will be computed. Each complete imputed data set will then be analyzed using simple proportions by treatment group ($p=x/N$, where x is the number of responder and N the number of subjects in this treatment group). The corresponding standard error for the sample proportion will be calculated with the square root of $p(1-p)/N$.

Note: For derivation of PASI75 response, the imputed PASI value will be compared directly to the observed Baseline PASI value to determine whether or not a reduction of at least 50% (or 75%, 90%, 100%) was achieved. If values outside of the pre-defined range

of values for PASI (0-72) are imputed, they will be cut off as appropriate after the multiple imputation procedure but before deriving the responder variables. For example, an imputed PASI value of -0.5 would be changed to 0 before deriving the PASI responder variable.

5. The results at each week of each of the 75 imputed data sets will be combined into a single inference using SAS PROC MIANALYZE.

The estimated responder rates at each week will be presented by treatment group based on the FAS.

Additionally, NRI will be used for imputation of missing data. Simple proportions will be calculated to estimate responder rates at each visit in the Maintenance Period (ie, Week 16 through Week 52). Responder rates based on observed case data will also be summarized.

A table summarizing the PASI75/PASI90 response rates (simple proportions) during Maintenance Period based on the subset of PASI75/PASI90 responders at Week 16 will also be provided (observed case, NRI and MCMC imputed data).

Line plots will be generated to present the percentages of responders over time by maintenance treatment group over time (from Week 16 to Week 52) based on MCMC imputed data.

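### The optimal initial dose is the first secondary objective, but no model-based Week 16 contrast of CZP 400mg Q2W with 200mg Q2W, with its confidence interval, is planned

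*SAP*

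**What the plan says.** The secondary objectives (Protocol 3.2, SAP 2.1.2) begin with "The optimal initial treatment dose for the treatment of moderate to severe chronic plaque PSO".

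The planned Week 16 comparisons for plaque subjects are as follows.

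- **PASI75 test (SAP 8.1.2):** "Each CZP dose will be compared against PBO to establish superiority over PBO and will be tested sequentially at an alpha of 0.025".
- **PASI75 odds ratio (SAP 8.1.2):** "confidence intervals are calculated for the odds ratio of each CZP dose versus placebo".
- **PASI75 risk difference (SAP 8.1.2):** "the difference in the proportion of responders between each CZP treatment group and PBO will be estimated", with 95% intervals combined over imputations. The same sentence plans an estimated responder rate for each arm.
- **PGA and PASI90 (SAP 8.2.1, 8.2.2):** each "will be analyzed for treatment effects using pairwise comparisons based on the same method as that for the primary efficacy variable".
- **DLQI and Itch (SAP 8.2.3, 8.2.4):** "Treatment group comparisons for each CZP treatment group vs placebo will be performed using an analysis of covariance" model. LS means and standard errors are shown for each arm.
- **Hypotheses (SAP 4.5):** all are superiority to placebo.
- **Time to response, DLQI MCID and remission (SAP 8.3.5, 8.3.7):** each dose against placebo.

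SAP 8.3.1 and 8.3.2 speak of comparing treatment groups at each visit, but refer back to the primary model, whose specified contrasts are those above.

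For the final maintenance analysis, each imputed data set is "analyzed using simple proportions by treatment group" (SAP 8.3.1), without a model.

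**The concern.** A stated objective about dose should have an output that addresses it. Here the inferential outputs answer whether each dose beats placebo, and leave the comparison between doses to the reader. The two placebo-referenced odds ratios are a poor substitute, because they share one placebo arm of 25 and their intervals cannot simply be set against each other. Arm-level responder rates are better, but they come without a combined standard error for the difference between doses.

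The rationale in Protocol 5.4 gives the question some weight. It says the earlier Phase 2 study was not designed to separate the two active arms, that the higher dose tended to do better, and that both doses would be evaluated further in the global Phase 3 studies and in this one. Of the 125 randomised plaque subjects, 100 carry the information.

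**Working it through.** **Inputs (Protocol 14.8.1).** PASI75 at Week 16: 75% (400mg Q2W), 70% (200mg Q2W), 15% (placebo). Target n: 50, 50, 25. Required n: 43, 43, 22. Two-sided alpha 0.025 per dose.

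**1. The plan's own power figure.** For 70% against 15% with 43 and 22:

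- pooled rate = (43 × 0.70 + 22 × 0.15)/65 = 0.514
- null SE = sqrt(0.514 × 0.486 × (1/43 + 1/22)) = 0.131
- alternative SE = sqrt(0.21/43 + 0.1275/22) = 0.103
- z = (0.55 - 2.241 × 0.131)/0.103 = 2.48, so power is 99.3%

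With a continuity correction it is 98.4%, and with Fisher's exact test 98.6%. At 50 and 25 it is 99.8% (Fisher 99.3%). For 75% against 15% every figure is higher. The stated values, at least 98% and above 99%, are reproduced. The sample size is sound for what it was built for, which is each dose against placebo.

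**2. The direct dose contrast at Week 16** (unadjusted, no missing data).

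- Difference = 0.75 - 0.70 = 0.05
- SE = sqrt(0.75 × 0.25/50 + 0.70 × 0.30/50) = sqrt(0.00795) = 0.0892
- 95% half-width = 1.96 × 0.0892 = 0.175, giving -12.5 to +22.5 points
- Odds ratio = (0.75/0.25)/(0.70/0.30) = 1.29, 95% CI 0.53 to 3.10
- Power for 5 points at two-sided 0.05 is about 8%; 80% power would need about 1,251 per arm

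**3. What is lost by working from the two odds ratios against placebo.** Each arm contributes 1/(n p q) to the variance of a log odds ratio:

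| Arm | 1/(n p q) |
|---|---|
| Placebo | 1/(25 × 0.15 × 0.85) = 0.314 |
| 200mg Q2W | 1/(50 × 0.70 × 0.30) = 0.095 |
| 400mg Q2W | 1/(50 × 0.75 × 0.25) = 0.107 |

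The variances against placebo are 0.409 and 0.420, about three quarters of each from placebo. Treating the two odds ratios as independent gives SE sqrt(0.409 + 0.420) = 0.91 for the dose contrast. The direct contrast has SE sqrt(0.095 + 0.107) = 0.45, about half.

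**4. Other plausible rates (assumption).** Suppose the Week 12 rates of the Phase 2 study in Protocol Table 5-2 applied with 50 per arm. PASI75 would give 8.2 ± 16.0 points, and PGA 19.9 ± 18.6 points. So the interval is not bound to be uninformative on every endpoint.

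**5. The maintenance tables.** SAP 3.5.9 and 3.6.1 place Week 16 escapers from 200mg Q2W in the 200mg/200mg group for the final analysis, and SAP 4.2 counts them as non-responders afterwards. None go to the 200mg/400mg Q4W group. Illustration (assumptions): 6 of 50 escape at Week 16, 22 are re-randomised to each regimen, and response is 80% in both. The 200mg/200mg group shows (22 × 0.80)/(22 + 6) = 17.6/28 = 63% against 80%, a 17-point gap with no difference between regimens. Limited to re-randomised subjects, the risk difference has a 95% half-width of 1.96 × sqrt(2 × 0.8 × 0.2/22) = 0.236, about 24 points.

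**The case against.** The best reply is that the doses can already be compared. Responder rates by arm and, for DLQI and Itch, LS means with standard errors are planned, and the placebo term cancels on subtraction. Counts by arm even allow an unadjusted interval. This stands: a reader who infers that the trial yields no estimate of the dose difference, or cannot address it even descriptively, goes further than the SAP allows. What is missing is narrower: the adjusted contrast, combined over imputations, with its own standard error.

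Second, the objective is worded as an assessment and promises no test. That also stands. A reader might infer that a powered comparison of doses was owed, or that the sample size is at fault; neither follows from the documents, and step 1 reproduces the power claims. The remedy is therefore an interval. Dose-specific safety and PK summaries, which are planned, will also inform the choice.

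Third, a reader might extend the point to maintenance and infer that the durability objective requires a 200mg Q2W versus 400mg Q4W contrast. The documents do not say so. The objective concerns durability under maintenance treatment, limiting post-Week 16 data to description is deliberate (Protocol 14.3, SAP 8), and responder rates to Week 52 address it. SAP 8.3.1 also has a combined-period table that shows the re-randomised groups apart from escapers. Nor could such a contrast be read off an existing model, since the final maintenance analysis has none. The caution in step 5 applies only if the blinded-maintenance tables are used to compare the two regimens.

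Fourth, timing. SAP 9.3 and 9.4 cite interim results, and SAP 4.3 and Table 8-4 show that the unblinded interim analysis already included the Week 16 primary and secondary analyses. A contrast added now is post hoc and must be labelled so.

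**Conclusion.** The point holds in limited form. The plan lists the optimal initial dose first among its secondary objectives, yet specifies no model-based 400mg Q2W versus 200mg Q2W contrast with a confidence interval at Week 16, and no statement of how the objective will be judged. It reports arm-level estimates and contrasts against placebo only.

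At the planning rates with 50 per arm and complete data, the missing interval is about -12.5 to +22.5 points. It is wide, and showing that width would itself tell the reader how little the trial can say about dose. Covariate adjustment and imputation would alter it somewhat. The primary analysis, the error control and the sample size are unaffected, and no view is taken here on which dose is preferable.

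**What to change.** **Week 16.** From the models already fitted, report 400mg Q2W versus 200mg Q2W with 95% CIs:

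- odds ratio and risk difference for PASI75, PGA and PASI90, combined over the 75 imputations; the variance formula in SAP 8.1.2 serves with the 200mg arm in place of placebo
- adjusted mean difference for DLQI and Itch from the existing ANCOVAs

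Label these as estimation only, outside the testing sequence, and added after the interim unblinding. Add a sentence saying how the dose objective will be judged from them.

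The cost is one contrast per Week 16 model, with no alpha spent and no further subjects. The downsides are wide intervals and the post hoc label.

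**Week 52 (optional, separate).** If 200mg Q2W and 400mg Q4W are compared, limit the comparison to re-randomised subjects and give a simple risk difference with CI. This is a small additional subset analysis, with an interval of roughly ±24 points under the assumptions in step 5.

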14.3.2 Other efficacy analyses

14.3.2.1 Analysis of the secondary efficacy variables for subjects with moderate to severe chronic plaque PSO

The secondary efficacy variables will be analyzed for all subjects in the FAS.

Secondary efficacy variables are PASI90, PGA response, and change from Baseline in DLQI at Week 16.

A subject will be classified as a PGA responder if the PGA is Clear or Almost clear with at least a 2-category improvement relative to Baseline. The analysis of PASI90 and PGA response at Week 16 will be analyzed for treatment effects using pairwise comparisons based on the same method as that for the primary efficacy variable.

The MCMC algorithm is based on the multivariate normal model; imputed values for PGA will not generally be one of the discrete values actually used in PGA scoring (0, 1, 2, 3, or 4).

Therefore, standard rounding rules will be applied to the imputed values in order to derive the binary PGA response variable. For example, if a subject has a PGA score imputed as 1.4 (and assuming a Baseline PGA score of 3), this imputed value would be rounded down to 1, and the minimum change from Baseline of 2 would have been met. Therefore, this subject would be considered a responder.

The significance testing of each CZP treatment group vs PBO will be part of the fixed sequential testing procedure described in Section 14.2.

The analysis of DLQI will be based on the change from Baseline at Week 16. Treatment group comparisons for each CZP treatment group vs PBO will be performed using an analysis of covariance (ANCOVA) model with treatment group and prior biologic exposure (yes/no) as factors and Baseline DLQI score as a covariate. The treatment differences and corresponding 97.5% confidence intervals will be calculated based on the adjusted means. Missing values will be imputed using last observation carried forward (LOCF). Each CZP dose will be compared against PBO to establish superiority over PBO and will be tested at an alpha of 0.025 as part of the fixed sequence testing procedure described in Section 14.2.

14.3.2.2 Analysis of the other efficacy variables for subjects with moderate to severe active plaque PSO

All other efficacy variables (eg, PASI50, PASI75, PASI90, PASI100, PGA, MCID) will be analyzed for all subjects in the FAS.

All categorical variables (eg, PASI score, PGA score, BSA score, DLQI) will be summarized using frequency tables by each visit.

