4.5 Multiple comparisons/multiplicity

The statistical analysis of the primary and selected secondary efficacy variables will account for multiplicity and control the familywise type I error rate at a 2-sided alpha level of 0.05 by using a fixed sequence testing procedure. The hypotheses are mapped into 2 sets (H1, H3, H5 and H7) and (H2, H4, H6 and H8) so that hypotheses within each set correspond to the same CZP dose. The type I error will be split equally between CZP 400mg Q2W and CZP 200mg Q2W, so that each dose will be tested at a 2-sided alpha level of 0.025.

The first 2 hypotheses for each dose (H1 for CZP 400mg Q2W; H2 for CZP 200mg Q2W) test whether the given CZP dose is superior to placebo for PASI75 response at Week 16. These are the hypothesis tests corresponding to the primary endpoint. If this is rejected at a 2-sided alpha level of 0.025, that alpha will be passed to the next test in the sequence, allowing the testing procedure to proceed.

The hypotheses associated with the subsequent tests are for secondary efficacy endpoints and are based on testing for superiority relative to placebo. See Figure 4–1 for details on this procedure.

Figure 4–1: Fixed sequence testing procedure

If all hypotheses within one set of hypotheses (either CZP 400mg Q2W or CZP 200mg Q2W) have been rejected, the corresponding type I error probability can be passed on to the other set of hypotheses and that set can be retested if necessary at a 2-sided alpha level of 0.05 (Bretz et al, 2009).

All significance tests are performed at an alpha level of 0.025.

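### SAP 8.1.2 reports risk differences only with 95% intervals although each dose is tested at 0.025, and SAP 8.2.3 leaves out the protocol's 97.5% level for the DLQI difference

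*SAP*

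**What the plan says.** **Test level.** SAP 4.5 splits alpha equally, "so that each dose will be tested at a 2-sided alpha level of 0.025", and adds "All significance tests are performed at an alpha level of 0.025". It also allows recycling: once every hypothesis for one dose has been rejected, the other dose has a set of hypotheses and "that set can be retested if necessary at a 2-sided alpha level of 0.05".

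**Risk difference.** SAP 8.1.2 specifies 95% for the difference in responder proportions, "2-sided 95% CIs will be created for each difference", and the imputed results are "combined into a single 2-sided 95% confidence interval using SAS PROC MIANALYZE". The fallback for a group with no responders or only responders also uses 95%. SAP 8.2.1 and 8.2.2 apply the primary method to PGA response and PASI90, so the level carries over to both.

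**Odds ratio.** SAP 8.1.2 gives formulas for both 95% and 97.5% limits but does not say which is reported for the sequence endpoints. Protocol 14.3.1 plans an odds ratio with an interval of unstated level and no risk difference.

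**DLQI.** Protocol 14.3.2.1: "The treatment differences and corresponding 97.5% confidence intervals will be calculated based on the adjusted means". SAP 8.2.3 tests DLQI at 0.025 but says only that "adjusted mean treatment differences, corresponding confidence intervals, and p-values will be reported". SAP 3.9, which lists changes to protocol-defined analyses, mentions only the analysis sets.

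**The concern.** An interval printed beside a confirmatory test is usually read as its counterpart. If the test uses 0.025 and the interval 95%, a result with p between 0.025 and 0.05 shows an interval clear of zero while the test at 0.025 fails. A reader of the report could take that as a positive finding.

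The DLQI gap is the more concrete part. The protocol fixed a level, and the SAP omits it without comment. The adjacent section, SAP 8.2.4 on the Itch scale, uses almost the same ANCOVA text with 95% written in. Itch is not in the protocol's testing sequence (Table 14-1). A programmer filling the blank in 8.2.3 could copy that 95%, contrary to the protocol.

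For the risk differences, the mismatch is between the SAP's interval level and the SAP's own alpha.

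**Working it through.** **1. The plan's own figures.** The alpha split adds up: 0.025 + 0.025 = 0.05. Protocol 14.8.1 assumes PASI75 rates of 75%, 70% and 15% and claims power of at least 98% with 43 against 22 subjects, and above 99% with 50 against 25, at 2-sided 0.025. Both claims reproduce:

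| Sample size | Method | 75% vs 15% | 70% vs 15% |
|---|---|---|---|
| 43 vs 22 | Normal approximation | 99.9% | 99.3% |
| 43 vs 22 | Fisher exact | 99.7% | 98.6% |
| 50 vs 25 | Normal approximation | 99.97% | 99.8% |
| 50 vs 25 | Fisher exact | 99.8% | 99.3% |

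The design was therefore sized at 0.025, and 97.5% is the matching interval level.

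**2. Width.** z(0.975) = 1.960 and z(0.9875) = 2.241. The ratio is 2.241/1.960 = 1.144, so a 97.5% interval is 14.4% wider. For the DLQI ANCOVA at about 121 degrees of freedom (125 subjects less 4 parameters beyond rounding for exclusions), t = 2.270 against 1.980.

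**3. DLQI.** Test and interval come from the same model and the same t statistic. A 97.5% interval excludes zero exactly when p < 0.025, and a 95% interval exactly when p < 0.05. The gap is p from 0.025 to 0.05, and restoring 97.5% closes it.

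**4. Risk difference.** The test is on the log odds ratio and the interval is on the difference in proportions. Without the covariate or imputation, the SAP's standard error reduces to √[p₁(1−p₁)/n₁ + p₂(1−p₂)/n₂]. The counts below are illustrative assumptions.

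| Placebo | CZP | log OR (SE) | p | Difference (SE) | 95% interval | 97.5% interval |
|---|---|---|---|---|---|---|
| 4/25 | 19/50 | 1.169 (0.618) | 0.059 | 22.0% (10.0%) | 2.3% to 41.7% | −0.5% to 44.5% |
| 4/25 | 20/50 | 1.253 (0.617) | 0.042 | 24.0% (10.1%) | 4.2% to 43.8% | 1.4% to 46.6% |
| 3/25 | 18/50 | 1.417 (0.682) | 0.038 | 24.0% (9.4%) | 5.6% to 42.4% | 2.9% to 45.1% |

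In the first row, 97.5% removes the disagreement with the test. In the other two it does not.

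Enumerating placebo counts of 1 to 5 out of 25 gives 25 count pairs where the 95% interval lies above zero but p exceeds 0.025. Moving to 97.5% resolves 8 of them, all with p above 0.05. It resolves none of the 12 with p between 0.025 and 0.05. So 97.5% aligns the nominal levels and reduces disagreement, but it does not make the risk-difference interval a substitute for the test.

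**5. Both doses together.** The two comparisons share the placebo arm. Assuming equal variances, their correlation is 50/(50+25) = 0.667, and bivariate normal joint coverage is 91.5% with 95% intervals and 95.6% with 97.5% intervals. Using the design rates instead, the variances are 0.15×0.85/25 = 0.00510, 0.75×0.25/50 = 0.00375 and 0.70×0.30/50 = 0.00420. The correlation is then 0.00510/√(0.00885×0.00930) = 0.56, and joint coverage is 91.1% and 95.4%.

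**6. How often it would matter for PASI75.** Power at 0.05 minus power at 0.025, under the design rates with 50 against 25, is 0.02% for 400 mg and 0.15% for 200 mg. The documents give no design rates for PGA, PASI90 or DLQI, so no such figure can be computed for them.

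**The case against.** Several points on the other side stand.

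- **The protocol's 97.5% covers DLQI only.** A reader might infer that the 95% risk-difference intervals breach a protocol level. They do not: the protocol plans no risk difference.
- **The primary test already has a matching interval available.** The odds ratio is the tested quantity, and SAP 8.1.2 provides its 97.5% limits. The risk difference is an additional estimate on which no hypothesis is decided. A marginal 95% interval there is a defensible reporting choice, though an incomplete one when shown alone.
- **A p-value between 0.025 and 0.05 need not end a dose's sequence.** Under recycling that dose can be retested at 0.05, and 95% is then the matching level.
- **Changing the level does not cure scale disagreement**, as step 4 shows. In addition, an endpoint later in the sequence can have an interval clear of zero and still not be testable, because an earlier endpoint failed.
- **Joint coverage is not promised.** The plan controls familywise error through the tests. Step 5 describes the two levels and is not evidence of a breach.
- **For DLQI the SAP is silent; it does not substitute another level.** The protocol's 97.5% is not displaced, and a mismatch arises only if 95% is filled in.

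What remains is that the SAP should say what the protocol says for DLQI, and should not give the risk differences only at a level that differs from its own alpha.

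**Conclusion.** The point holds as a minor reporting matter. SAP 8.1.2 gives the PASI75, PGA and PASI90 risk differences only at 95% although SAP 4.5 tests each dose at 0.025. SAP 8.2.3 omits the protocol's DLQI level without declaring a change.

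The size is a factor of 1.144 in interval width. For DLQI there is also a p-value range of 0.025 to 0.05 in which a 95% interval and the test would disagree. For PASI75 at the assumed rates, that range would be reached with probability 0.15% or less.

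A reader might infer inflated type I error or an unsound success criterion. The documents do not support that: success rests on p-values in the fixed sequence, so error control, power and sample size are untouched.

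The arithmetic rests on normal approximations, on illustrative counts without covariate or imputation, and on a stated correlation for the joint-coverage figures.

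**What to change.** - **SAP 8.2.3:** write 97.5% for the DLQI treatment difference, as in protocol 14.3.2.1. If another level is intended, declare it in SAP 3.9.
- **SAP 8.1.2, and through it 8.2.1 and 8.2.2:** report 97.5% intervals for the odds ratios and risk differences of the endpoints in the sequence. Keep 95% beside them, labelled as nominal and as the matching level for a dose retested at 0.05. Showing both avoids making the reported level depend on the other dose's results.
- **SAP 4.5 or 8.1.2:** state that the p-value within the sequence decides success, and that the risk-difference interval is on a different scale from the log-odds-ratio test and can disagree with it at either level. Qualify the closing sentence of 4.5 on the 0.025 level so that it allows for the retest at 0.05.

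The cost is SAP wording and extra table columns. The downside is that the 97.5% intervals are 14% wider. No new data are needed, and type I error, power and the decision rule do not change.
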